## **Source of Subjects and Recruitment Methods**

To maximize enrollment of subjects with anorexia nervosa, a number of referral mechanisms have been put into place over the past years utilizing the strong relationships with directors of area eating disorder programs, as well as a regional network of health care providers -- The New England Eating Disorders Research Collaborative. Subjects will be recruited from a large population of patients with anorexia nervosa from the following locations and through the following resources:

1) New England Eating Disorders Research Collaborative was established at MGH several years ago and meets regularly for two hours each session to discuss recruitment strategies for MGH anorexia nervosa studies, review MGH research findings and discuss published data from other groups. This group represents a concerted and collaborative effort to recruit subjects with anorexia nervosa to the MGH studies and funnels patients into these studies from all over the New England area. It has been developed into an effective recruitment tool. The group includes representatives from the leadership of major eating disorder treatment centers and groups in the larger area, including: [REDACTED]

[REDACTED]

[REDACTED]

[REDACTED]

2) The Eating Disorders Clinical and Research Program (EDCRP) at Massachusetts General Hospital, which is the largest operating eating disorders clinic in New England. The Eating Disorders Unit in the Massachusetts General Hospital Child Psychiatry Service and the Adult Eating and Weight Center together form the largest outpatient Eating Disorders Clinic in the New England area. The EDCRP sends out biannual newsletters that inform clinicians and families of eating disordered patients about new research opportunities. Their web-site is a frequently hit ED site, and details about the study will be available on that site. The EDCRP networks regularly with major treatment centers for eating disorders in Connecticut, Vermont, Rhode Island, New Hampshire, and Maine and with the 250 college health centers in the Greater Boston area.

3) Walden Behavioral Care. The Neuroendocrine Unit is invited to give monthly educational talks to patients and provide information about ongoing studies at the inpatient, partial hospitalization and residential programs.

4) The Massachusetts Eating Disorders Association, which runs support groups for women with eating disorders throughout eastern Massachusetts.

5) Health services at local colleges and universities, including Boston University and Harvard University Health Services.

6) Recruitment through local university job boards, including Boston University, Northeastern University, and Harvard University

7) Social media posts (Twitter, Instagram, Facebook, etc.)

8) Mass General Brigham Rally online platform.

9) Mass General Brigham Research Study Volunteer Program (RSVP for Health).

10) Mass General Brigham Research Patient Data Registry (RPDR) and Mass General Brigham Patient Gateway. Additional recruitment will involve the Mass General Brigham Research Patient Data Registry (RPDR), which allows targeted searches of patients within the Mass General Brigham system by age, sex, and diagnosis with the ability to filter out patients by study-specific exclusion criteria. This results in a highly targeted recruitment list that allows investigators to contact potential subjects following the new OPT-OUT model. Using a targeted recruitment list from RPDR, which will exclude patients who have opted out of research invitations, we will send recruitment letters to potential subjects through Patient Gateway following the new OPT-OUT model. Additionally, we may mail recruitment letters to potential research subjects identified through RPDR who are not active on Patient Gateway.

11) Recruitment through Handshake, an online platform that connects students at universities and colleges to employers to find job opportunities.

12) Recruitment through flyers posted at local college and university campuses, community centers, and other public spaces.

13) Recruitment through a list of research subjects who have previously been recruited by our study team and who have agreed to be recontacted for future studies.

#### **IV. Subject Enrollment**

Informed consent will be obtained from all potential study subjects by a licensed physician investigator or nurse practitioner investigator before any procedures are performed. At this time, the subject will be explicitly counseled that she is free to choose whether or not to participate in this study.

Eligible subjects will be randomized at the baseline visit to the treatment or placebo group. Neither the investigator nor the subject will be aware to which group she is assigned until after the study is completed and has been un-blinded or in the case of significant safety considerations for a specific subject.

All subjects will receive a single intravenous infusion of open-label zoledronic acid at the month 12 study visit.

#### **V. STUDY PROCEDURES**

**Screening Visit:** A “Screening Visit” will be conducted by a member of the study clinical team to determine eligibility for the protocol. All subjects will be seen at Massachusetts General Hospital (MGH) for an outpatient visit including the following: A complete medical history including eating disorder, weight, medication, consumptive habits (smoking, alcohol, caffeinated beverages), and menstrual history will be taken. In addition, the following will be performed:

1. A clinical evaluation, including temperature, pulse, blood pressure, and a urine pregnancy test. Women will be exempt from urine pregnancy tests if they are in menopause or if they have had any well-documented method of surgical sterilization, including hysterectomy, bilateral oophorectomy, and tubal ligation. A physical and oral examination will also be performed.
2. Blood draw for comprehensive metabolic panel, CBC, magnesium, direct LDL, and 25-OH vitamin D, if not performed clinically within 6 weeks prior to the screening visit. Additional blood will be drawn to enable testing repeat in cases of lab error or tube breakage.
3. Nutritional evaluation, including weight in a gown, height, frame size, calculation of percent IBW and body mass index (BMI)
4. DXA scan of the spine, hip, radius, and total body for BMD and body composition, including lean mass, is required if the subject has not had a DXA scan within 6 months prior to the screening visit and optional if she has had one
5. Verification of the anorexia nervosa diagnosis and determination of anorexia nervosa subtype (restricting or binge/purge) using DSM-V criteria
6. Verification of lack of severe comorbid concerns (i.e. suicidality, substance use) that would preclude safe study participation will occur by the study psychologist or psychiatric nurse

practitioner. Suicidality is assessed through a verbal conversation with a psychiatric health professional. If the subject has been suicidal in the past, the psychiatric professional will ask questions to assess their level of suicidality, and whether it would be a risk to their health to partake in a study. If a subject appears to be actively suicidal, study staff will make appropriate referrals, which will often include the Acute Psychiatric Service at MGH; all efforts will be made to contact the subject's clinical treatment team.

7. Plain film of wrist/hand to determine bone age in women with primary amenorrhea who have not received estrogen for  $\geq 1$  year.
8. Electrocardiogram (ECG or EKG) to assess cardiovascular risk.

If the 25-OH vitamin D level at the screening visit is not  $>30$  ng/ml, participants will be given one loading dose of oral vitamin D3 (cholecalciferol) 5,000 IU daily and the 25-OH vitamin D level will be checked every 3 weeks until their 25-OH vitamin D level meets the eligibility requirement ( $>30$  ng/ml).

**Baseline Visit:** Eligible study subjects (n=30 women with anorexia nervosa or atypical anorexia) will be assessed at an outpatient visit at MGH for baseline testing.

1. A clinical and bionutrition evaluation and urine pregnancy test (unless exempt from urine hCG).
2. DXA scan of the spine, hip, radius, and total body for BMD and body composition, including lean mass, if screen visit did not take place within 6 weeks of baseline visit or if a DXA scan was not performed at the screening visit.
3. Baseline hormone and safety blood testing, if not performed clinically within 2 weeks prior to the baseline visit.
4. HR-pQCT and FEA of the radius and tibia
5. Eating Disorder Examination—Questionnaire
6. Eating Disorder Inventory-3
7. Paffenbarger Exercise Questionnaire
8. Calcium and vitamin D food frequency questionnaire

Randomization to treatment or placebo group will occur at the baseline visit. Twenty subjects will be randomized to active romosozumab (210 mg, which must be administered as two injections of 105 mg) and 10 subjects will be randomized to identical placebo injections. In the rare case that a subject withdraws from the study after being randomized but prior to completing the baseline visit, we will replace such dropouts with the goal that thirty subjects will complete the baseline visit. Randomization will be stratified for presence or absence of atypical anorexia nervosa, defined as  $BMI \geq 18.5$  kg/m^2 vs.  $< 18.5$  kg/m^2. Subjects will return every month over the following 12 months to receive ongoing injections.

If screen 25-OH vitamin D level is  $<40$  ng/ml, subjects will be given one loading dose of oral vitamin D2 (ergocalciferol) 50,000 IU at the baseline visit. All subjects will be asked to take a standard dose of 1000 mg calcium and 800 IU vitamin D supplements daily throughout the study. It is our experience from multiple clinical trials that women with anorexia nervosa are extremely compliant with calcium and vitamin D supplementation.

After the baseline visit, follow-up visits will occur at monthly intervals during the first 12 months of the study so that the romosozumab or placebo injections can be administered by a study physician, nurse practitioner, or study nurse. In rare cases where subjects are unable to travel to MGH, the study

injections may be mailed to and administered by an out-of-state, licensed physician, physician assistant, or nurse practitioner responsible for the clinical care of the study subject. A urine pregnancy test (unless exempt from urine hCG) and clinical evaluation will be performed at each monthly visit. A bionutrition evaluation, including weight in a gown, height, and calculation of percent IBW and body mass index (BMI), will be performed at months 3, 6, 9, and 12. At months 1, 3, 6, 9, and 12, blood testing, including for electrolytes (e.g. calcium), will occur unless performed clinically within 2 weeks prior to the study visit. Calcium and eGFR must be normal and 25-OH vitamin D must be  $> 20$  ng/mL at the most recent visit in order to receive zoledronic acid at the 12-month visit. If labs are not normal, study staff will reach out to the participant's care team to assist with timely intervention with the goal that repeat labs are normal prior to the 12-month visit. Participants with serum 25-OH vitamin D  $\leq 20$  ng/ml at the 9-month visit will be given oral vitamin D2 (ergocalciferol) 50,000 IU weekly, and their 25-OH vitamin D level will be rechecked at the 11-month visit. If their repeat serum 25-OH vitamin D level at the 11-month visit is still  $\leq 20$  ng/ml, we will continue to provide oral vitamin D2 (ergocalciferol) 50,000 IU weekly, and their 25-OH vitamin D level will be rechecked every 2 weeks until their 25-OH vitamin D level meets the requirement ( $> 20$  ng/ml) to receive zoledronic acid. Additionally, participants will be given one loading dose of oral vitamin D2 (ergocalciferol) 50,000 IU at the 12-month visit if their most recent 25-OH vitamin D level is  $< 30$  ng/ml. At months 3, 6, 9 and 12, questionnaires will be completed (EDI-3 and EDE-Q). Additionally, at months 6 and 12, a Paffenbarger exercise questionnaire will be completed. A calcium and vitamin D food frequency questionnaire will be completed at the month 12 visit as well. DXA at the spine, hip, radius and total body for BMD and body composition, including lean mass, will be performed 6 and 12 months after baseline. HR-pQCT and FEA of the radius and tibia will be performed at 6 and 12 months. Markers of bone metabolism will be measured at months 3, 6, 9 and 12.

A clinical evaluation and pregnancy test (unless exempt from urine hCG) will be performed at the 18 and 24-month visits, as will a nutrition evaluation, including weight in a gown, height, and calculation of percent IBW and body mass index (BMI) and completion of questionnaires (EDI-3, EDE-Q, and Paffenbarger exercise questionnaire). A calcium and vitamin D food frequency questionnaire will also be administered at the month 24 visit. At 18 and 24 months, markers of bone metabolism will be measured, and safety labs will be performed, unless performed clinically within 2 weeks prior to the study visit. DXA at the spine, hip, radius and total body will be performed at the 24-month study visit. HR-pQCT and FEA of the radius and tibia will also be performed at 24 months.

For the 18-month visit, subjects who do not live locally will be permitted to have their blood drawn and pregnancy test performed offsite for lab tests required for the visit. Tests that need to be run in real time will be done at local laboratories, with the results provided online to investigators. Otherwise, the samples will be mailed to investigators. Subjects who choose this option will also have an interim history performed by our staff by telephone.

Additionally, for all visits which involve questionnaires, those will be completed on paper during the visit or sent electronically via Redcap to be completed and returned to study staff.

Study Visit	Screen	Baseline	M1	M2	M3	M4	M5	M6	M7	M8	M9	M10	M11	M12	M18	M24
Consent	X															
Clinical assessment	X	X			X			X			X			X	X	X
HCG	X	X	X	X	X	X	X	X	X	X	X	X	X	X	X	X
Safety Labs (CBC, magnesium, and CMP at screen; BMP, calcium, magnesium, and albumin thereafter)	X	X	X		X			X			X			X	X	X
Study drug (romosozumab) or placebo injection			X	X	X	X	X	X	X	X	X	X	X			
Zoledronic acid infusion														X		
Nutrition Evaluation (height, weight)	X	X			X			X			X			X	X	X
Bone Markers (CTX, P1NP, osteocalcin)			X		X			X						X	X	X
IGF-1			X					X						X		
25-OH VitD	X										X					
Direct LDL	X															
Electrocardiogram (ECG or EKG)	X															
BMD (DXA)	X	X						X						X		X
Bone Strength with FEA (Xtreme CT)		X						X						X		X
EDI-3			X		X			X			X			X	X	X
EDE-Q			X		X			X			X			X	X	X
Paffenbarger Questionnaire (exercise quantification)			X					X						X	X	X
Calcium and Vitamin D Food Frequency Questionnaire			X											X		X

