## II. Specific Aims

### Phase 1: Romosozumab vs placebo

This █-sponsored investigator-initiated protocol is a randomized, double-blind, placebo-controlled clinical trial which aims to investigate the effect of romosozumab on BMD in women with anorexia nervosa. We will also investigate the safety of romosozumab in women with anorexia nervosa. We hypothesize that 12 months of romosozumab administration will result in an increase in bone mineral density, increase in markers of bone formation and decrease in markers of bone resorption, and improvement in bone microarchitecture in osteopenic women with anorexia nervosa compared with placebo.

**Specific Aim 1:** We hypothesize that 12 months of romosozumab administration will result in an increase in bone mineral density in women with anorexia nervosa with low bone mass or osteoporosis compared with placebo.

We will investigate in women with anorexia nervosa in a 12-month study whether treatment with romosozumab will increase BMD as measured by dual energy x-ray absorptiometry (DXA) compared with placebo. The primary endpoint will be change in lumbar spine BMD from baseline to 12 months. Bone density will be measured at baseline, 6 months and 12 months.

**Specific Aim 2:** We hypothesize that 12 months of romosozumab administration will result in a significant increase in markers of bone formation and reduction of markers of bone resorption in osteopenic women with anorexia nervosa compared with placebo.

We will investigate in women with anorexia nervosa in a 12-month study whether markers of bone formation, including osteocalcin and P1NP, will increase in the romosozumab group more than in the placebo group. We will also investigate whether markers of bone resorption, including CTx, will decrease in the romosozumab group more than in the placebo group. Markers of bone metabolism will be measured at baseline, 3 months, 6 months, 9 months and 12 months.

**Specific Aim 3:** In this exploratory aim, we hypothesize that 12 months of romosozumab administration will result in improved bone microarchitecture and strength in osteopenic women with anorexia nervosa compared with placebo.

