**Exclusion Criteria:**

- Hospitalization within 3 months of baseline study visit, including inpatient eating disorder treatment facility; participating in a residential eating disorder treatment program within 3 months of study participation is permitted
- Myocardial infarction or stroke within 1 year preceding enrollment
- History of hypertension or use of anti-hypertensive medications within the past 6 months
- Any disease known to affect bone, including untreated thyroid dysfunction, Cushing's or renal failure
- Any medication known to affect bone metabolism within 3 months of the study, excluding oral contraceptives or other forms of estrogen administration. Bisphosphonates must have been discontinued for at least one year before participation
- Immunodeficiency or taking immunosuppressive therapy
- Serum 25-OH vitamin D level  $<30 \text{ ng/mL}$
- Serum potassium  $<3.0 \text{ meq/L}$
- Serum magnesium  $<1.5 \text{ meq/L}$
- Serum ALT  $>3$  times upper limit of normal
- eGFR of less than 30 ml/min
- LDL  $> 190 \text{ mg/dL}$
- Hypocalcemia
- Diabetes mellitus
- Active substance abuse, including alcohol
- Current smoker
- History of malignancy
- Paget disease of bone
- Osteomalacia

- Osteonecrosis of the jaw (ONJ) or risk factor for ONJ, such as invasive dental procedures (eg, tooth extraction, dental implants, oral surgery in the past 6 months), poor oral hygiene, periodontal and/or pre-existing dental disease, and current use of corticosteroids.
- Planned invasive dental procedure over the next 24 months
- Known sensitivity to any of the products or components of the medication to be administered
- Sensitivity to calcium or vitamin D supplements
- Pregnant, planning to become pregnant within 12 months after the end of treatment and/or breastfeeding
- Subjects with a known esophageal disease
- Abnormalities of the esophagus such as stricture or achalasia
- Inability to sit/stand upright for at least 30 minutes
- Hypersensitivity to any component of zoledronic acid

**Drop Criteria (conditions for withdrawing subjects). These criteria (other than pregnancy) apply until the zoledronic acid infusion has occurred:**

- Pregnancy (for any subject)
- BMI < 16.0 kg/m^2 at two consecutive study visits at which weight and height are measured
- Hospitalization, including inpatient eating disorder treatment facility; participation in a residential eating disorder treatment program is permitted

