## VI. Biostatistical Analysis

**Sample Size and Justification:** Group sample sizes of 20 (active therapy) to 10 (placebo) for a total N=30 will achieve 80% power to reject the null hypothesis of equal means when the population mean difference is at least 9% with a standard deviation between groups of 8% and with a significance level of (alpha) of 0.050 using a 2-sided 2-sample equal-variance t-test. This is based on the difference in percent change in spine bone density between the romosozumab (n=65) and placebo (n=61) groups in Cosman F. *et al.*.

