### **Data Analysis Plan:**

The data analysis plan for the study will be as follows. The primary analysis will be intention-to-treat, with the primary endpoint being change in PA lumbar spine aBMD. Statistical significance will be defined as a two-tailed p-value of  $\leq 0.05$ .

Phase 1 Aims 1-3: Baseline mean clinical characteristics between the 2 groups will be compared by t-test. Variables will be tested for normality using the Shapiro-Wilk test, and if non-normal, variables will be log-transformed before analysis. If the distribution remains non-normal after log-transformation, nonparametric testing using the Wilcoxon rank sum test will be performed instead. The analysis of variables at 12 months will be performed using a linear random effects model to estimate and test the effects of the 2 randomization groups (romosozumab vs placebo) from baseline to 12 months on the study endpoints.

Phase 1 Aim 4: The analysis of variables at 12 months will be performed using a linear random effects model to estimate and test the effects of the 2 randomization groups (romosozumab vs placebo) from baseline to 12 months on the study endpoints. We will also add a lean body mass x randomization group interaction term to examine if the effects of body mass change differ between romosozumab and placebo.

Phase 2 Aim 1: The analysis of variables at 24 months will be performed using a linear random effects model to estimate and test the effects of the 2 randomization groups (12 months of romosozumab followed by a single intravenous infusion of open-label zoledronic acid vs 12 months of placebo followed by a single intravenous infusion of open-label zoledronic acid) from baseline to 24 months on the study endpoints.

Phase 2 Aim 2: A secondary analysis will be performed to determine whether gains achieved in the romosozumab group are maintained through the subsequent 12-month study period using a linear random effects model with the fixed effect being time and the random effect being the intercept. Lack of statistical significance will indicate maintenance (lack of decrease--or increase) of BMD.

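### Randomisation is stratified by BMI (18.5 kg/m² or above vs below), but the between-group models do not name the stratum: a minor efficiency point

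*Combined protocol and SAP*

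**What the plan says.** Section V, Baseline Visit: "Randomization will be stratified for presence or absence of atypical anorexia nervosa", with the boundary at a BMI of 18.5 kg/m². Twenty women go to romosozumab and ten to placebo.

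Section VI, Data Analysis Plan, Phase 1 Aims 1-3: a "linear random effects model to estimate and test the effects of the 2 randomization groups (romosozumab vs placebo) from baseline to 12 months". Phase 2 Aim 1 has the same form: "The analysis of variables at 24 months will be performed using a linear random effects model to estimate and test the effects" of the two sequences from baseline to 24 months. Neither paragraph names the stratum or any baseline covariate, and the stratum appears nowhere else in Section VI. The one extra term named for a between-group model is the lean mass by group interaction in Phase 1 Aim 4.

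The sample size paragraph assumes that the "population mean difference is at least 9% with a standard deviation between groups of 8" percent, with a two-sided equal-variance t-test at 0.05. Section II, Phase 1 Aim 1 gives the DXA schedule: "Bone density will be measured at baseline, 6 months and 12 months". Section V adds that "DXA at the spine, hip, radius and total body will be performed at the 24-month study visit".

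**The concern.** Stratified allocation balances the factor between arms, so the treatment estimate is already protected from chance imbalance in it. A model that ignores the factor does not credit that protection. Variance between strata stays in the residual, the reported standard error exceeds the true one, and the test rejects a true null less often than 5%.

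What is at stake is precision, in a trial with only ten women on placebo. Validity is not in question. The form of the term also matters. The plan does not say whether baseline BMD is a response or a covariate. If it is a response in a random-intercept model, a stratum main effect shifts all of a woman's visits equally and cancels from her change. A bare instruction to add the stratum could then achieve nothing.

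**Working it through.** **1. The plan's own figure.** Inputs from the sample size paragraph: 20 vs 10, difference 9, SD 8, two-sided 0.05.

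- SE = 8 × √(1/20 + 1/10) = 8 × 0.3873 = 3.098
- Noncentrality = 9 / 3.098 = 2.905, with 28 degrees of freedom
- Power = 80.06%, matching the stated 80%.

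**2. Assumptions beyond the documents.** The documents give no stratum gap in mean BMD change and no stratum sizes. The gap is therefore varied from 0 to 8 percentage points, the smaller values being the more plausible. Strata are taken as 15/15 (or 21/9 where stated), with 2:1 allocation within each. The total SD of change is held at 8. Data are complete unless stated.

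**3. Mechanism at a gap of 4, strata 15/15.**

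- Between-stratum variance = 4²/4 = 4, so within-stratum variance = 64 − 4 = 60.
- True SE of the treatment difference = √(60 × 0.15) = 3.00.
- Expected residual variance without the stratum = (28 × 60 + 30 × 4)/28 = 64.3, so the reported SE is about √(64.3 × 0.15) = 3.11.

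The reported SE is about 3.5% too wide.

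**4. Change-score model (200,000 replicates per gap, strata 15/15).**

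| Gap | Power without stratum | Power with stratum | Type I error without |
|---|---|---|---|
| 0 | 80.2% | 80.1% | 5.0% |
| 2 | 80.0% | 80.3% | 4.9% |
| 4 | 80.6% | 82.4% | 4.3% |
| 6 | 81.4% | 85.5% | 3.5% |
| 8 | 82.8% | 89.9% | 2.4% |

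With strata of 21/9 the gains are −0.1, 0.3, 1.5, 3.4 and 6.2 points. Absolute bias is below 0.02 points.

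**5. Random-intercept model, closer to the plan (40,000 replicates per gap).** Visits are 0, 6 and 12 months for Phase 1, and 0, 6, 12 and 24 for Phase 2. Further assumptions: the month-6 gap is half the month-12 gap, the month-24 gap equals it, residuals are independent, and the same 9 and 8 apply at month 24. The contrast is the group difference in change.

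| Gap | Month 12, without / with stratum-by-visit | Month 24, without / with |
|---|---|---|
| 0 | 81.5 / 81.4% | 82.0 / 81.9% |
| 2 | 82.1 / 82.3% | 82.3 / 82.5% |
| 4 | 82.7 / 83.6% | 83.7 / 84.5% |
| 6 | 84.7 / 86.6% | 85.5 / 87.2% |
| 8 | 87.7 / 90.9% | 88.5 / 91.2% |

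Type I error without the stratum is 5.1, 4.9, 4.5, 4.1 and 3.5% across the gaps, and about 5% with it. At a gap of 4 the month-12 SE is 3.04 without the stratum, 3.04 with a main effect only, and 2.99 with stratum-by-visit.

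**6. Dropout.** Replacement covers only withdrawals before the baseline visit is complete ("we will replace such dropouts with the goal that thirty subjects will complete the baseline visit"). Later losses are foreseen under "Drop Criteria (conditions for withdrawing subjects").

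- Change-score model, 6 of 30 lost at random: power without vs with the stratum is 69.5 vs 68.8% at gap 0, 69.4 vs 69.5% at gap 2 and 69.7 vs 71.6% at gap 4.
- Change-score model, deliberately uneven 24 completers (active/placebo 8/5 and 9/2 in the two strata), gap 0: 66.7 vs 64.3%.
- Random-intercept model, 6 of 30 lost at random, half of them expected to keep month 6 (6,000 replicates): 73.9 vs 73.6%, 72.7 vs 72.7% and 73.9 vs 74.5% at gaps 0, 2 and 4.

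**The case against.** The best case against acting is that the point is too small. In the planned type of model the gain is under one power point at gaps up to 4, and with dropout it runs from about −0.3 to +0.6, close to simulation noise. Nothing in the documents says that BMI around 18.5 predicts BMD change. A gap of 8 would nearly equal the whole assumed treatment effect of 9. The plan is also a short summary for a 30-woman pilot, silent on covariance structure and baseline handling too, and its silence on the stratum contradicts nothing.

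All of that stands as a statement of size, and it is why this is only a suggestion. It does not remove the point. The conservatism also appears in the random-intercept model, where type I error falls to 4.5% at a gap of 4. The stratum is already collected, and stating the term in advance closes off a choice of covariates after unblinding. The adjustment is not costless under dropout, and that should be weighed openly.

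**Conclusion.** The point holds as a minor efficiency matter. The trial stratifies its randomisation and then does not say that the between-group models use the stratum. No stated figure is wrong: the 80% power reproduces, type I error is at or below 5%, and there is no bias on average with complete data or random dropout.

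The expected benefit is 0 to 2 power points in a change-score model at gaps of 0 to 4, and roughly half that in the random-intercept model. It could be nil. This rests on assumed gaps, stratum sizes and near 2:1 allocation within strata. The Aim 4 interaction model was not examined, and Phase 2 Aim 2 is a within-group analysis to which the point does not apply.

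**What to change.** Before unblinding, add one sentence to the Data Analysis Plan naming the BMI stratum, as randomised, in the models for Phase 1 Aims 1-3 and Phase 2 Aim 1. The form should follow how baseline is handled:

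- (a) if change from baseline is modelled, stratum as a fixed effect;
- (b) if baseline is kept as a response in the random effects model, stratum plus stratum-by-visit.

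State that the treatment effect is the group contrast in change at month 12 (Phase 1) or month 24 (Phase 2). The same sentence should say whether the stratum is used when the rank-sum fallback applies.

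No new data are needed. Form (a) uses one degree of freedom; form (b) uses one per post-baseline visit for the change contrasts. In the change-score model, if the stratum is not prognostic and allocation stays near 2:1 within strata, the cost is about 0.1 power point (mean 95% CI width 12.58 to 12.59). It is about 0.7 point with 6 of 30 lost at random, and 2 to 3 points if dropout leaves the strata badly unbalanced.

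Adjusting for the baseline value of the endpoint is a separate choice and not part of this change. On its own it moves power from 80.1 to 78.5% if baseline is uncorrelated with change, 80.0 to 79.9% at a correlation of 0.2, and 80.4 to 85.1% at 0.4.
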